2.2.2. Governance

Eli Lilly and Company will be responsible for the selection of interventions to be added to, or removed from, clinical development on this platform trial. Lilly or a designee will provide the interventions to the study sites.

An IAC will be established for the purpose of making periodic prespecified or ad hoc assessments of safety data in an unblinded fashion and to make recommendations for protocol modifications or other actions. This internal committee will be independent of the Lilly study team.

In addition, an internal or external (independent) CEC may be established, if so specified in an ISA, for the purpose of adjudicating defined clinical events, in a blinded, consistent, and unbiased manner throughout the course of a study.

These and other governance considerations are further described in Appendix 10.1, Section 10.1.5.

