8.2. Safety Assessments

Visits and order of safety assessments

Safety assessments occur at visits specified in this master IMMA protocol SoA (Section 1.3) and in the SoA of the relevant ISA.

If multiple safety assessments are scheduled to occur at the same visit, the preferred order of completion is

- 1) QIDS-SR16, ECG, and then vital signs,
- 2) other safety assessments, including physical examinations, CXR, and nonleading (spontaneous) AE collection, followed by C-SSRS (Section 8.3.1.1), and finally
- 4) sample collection for clinical laboratory, PK, PD, pharmacogenetic, biomarker, and immunogenicity testing.

Data collection and reporting

The AE data collection and reporting requirements are described in Section 8.3 and Appendix 10.3.

For some interventions studied under this master protocol, there may be predefined AESIs. If so, the additional sample or data collections for AESIs will be specified in the ISAs.

Investigator safety monitoring

The principle investigator will monitor the safety data throughout the study. Immediate safety concerns should be discussed with the sponsor immediately upon occurrence or awareness to determine if the participant should continue or discontinue study intervention.

Sponsor safety monitoring

The sponsor will monitor the safety data, including AEs and SAE, discontinuations, vital signs, and clinical laboratory results by means of periodic blinded reviews and by other appropriate

methods. The SAE reports will be reviewed in real time and across studies and will include review of applicable clinical safety and epidemiological publications from the literature. If this safety monitoring activity uncovers an issue that needs to be addressed by unblinding at the individual or group level, members of the IAC can conduct additional analyses of the safety data. The IAC is an advisory group for this study formed to protect the integrity of the study in unblinded safety data reviews. See Appendix 10.1, Section 10.1.5.

Appropriateness of safety assessments

The safety assessments used in this study are routine elements of clinical health assessment and drug development.

Safety assessments described in this master protocol and in ISAs

The following sections describe safety assessments applicable to all ISAs.

See the ISAs for any additional safety assessments which may be applicable to a particular ISA.

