10.1.5. Committees Structure

Eligibility Review Committee

An eligibility review committee, also called adjudication panel, will review study entry data to ensure that prospective study participants meet the study entry criteria, particularly SLE disease activity criteria, prior to randomization. In addition, the committee will help ensure that high quality data are entered into the EDC system for the lupus assessments. The committee may include members of a third-party organization, members of the study team, and external SLE consultants as needed. Membership, responsibilities, operations, and measures to maintain confidentiality will be described in a committee charter.

Internal Assessment Committee (IAC)

In addition to safety reviews routinely performed by the sponsor as described in Section 8.2, the IAC will review the safety data in an unblinded fashion periodically or on an ad hoc basis during the study and will determine whether any changes (for example, dose reductions or other protocol modifications) should be made. If an efficacy interim analysis is specified in an ISA, the IAC will also be responsible for review of the available efficacy data.

The IAC reviewing the interim data will include, at a minimum, a Lilly medical physician, a statistician, and a representative from the Lilly Global Patient Safety organization, but will not include any Lilly study team members. Details about the IAC membership, purpose, responsibilities, and operation will be described in an IAC charter, which will be approved prior to the first unblinding.

Investigator sites will receive information about interim analysis results only if they need to know for the safety of their study participants.

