10.10. Appendix 10: Abbreviations and Definitions

Term	Definition
ACR	American College of Rheumatology
ADA	anti-drug antibodies
AE	adverse event
AESI	adverse events of special interest
AIDS	acquired immune deficiency syndrome
ALC	absolute lymphocyte count
ALP	alkaline phosphatase
ALT	alanine aminotransferase
ANA	antinuclear antibody
ANC	absolute neutrophil count
anti-dsDNA	anti-double stranded DNA
anti-HBc	antibody to hepatitis B core antigen
anti-HCV	antibodies to HCV
anti-Sm	anti-Smith antibodies
AST	aspartate aminotransferase
BCG	Bacillus Calmette-Guerin
BILAG 2004	British Isles Lupus Assessment Group 2004
blinding	A double-blind study is one in which neither the participant nor any of the investigator or sponsor staff who are involved in the treatment or clinical evaluation of the participants are aware of the treatment received.
CBD	cannabidiol
CDC	Centers for Disease Control and Prevention
CEC	clinical events committee
CFR	Code of Federal Regulations
CLASI	Cutaneous Lupus Erythematosus Disease Area and Severity Index

CMV cytomegalovirus

complaint A complaint is any written, electronic, or oral communication that alleges deficiencies

related to the identity, quality, purity, durability, reliability, safety or effectiveness, or

performance of a drug or drug delivery system.

compliance Adherence to all study-related, good clinical practice (GCP), and applicable regulatory

requirements.

CONSORT Consolidated Standards of Reporting Trials

CRF case report form

CRO contract research organization

CSR clinical study report

C-SSRS Columbia – Suicide Severity Rating Scale

CT computerized tomography

CTA clinical trial agreement

CXR chest x-ray

device deficiencies equivalent to product complaint

DNA deoxyribonucleic acid

DSM-V Diagnostic and Statistical Manual of Mental Disorders. 5th ed.

EBV Epstein-Barr virus

ECG electrocardiogram

eCRF electronic case report form

EDC electronic data capture

eCOA electronic Clinical Outcome Assessment

eGFR estimated glomerular filtration rate

EMA European Medicines Agency

enroll/enrollment Treatment assignment; the act of assigning a participant to a treatment. Participants who

are enrolled in the study are those who have been assigned to a treatment.

enter Participants entered into a study are those who sign the informed consent form directly

or through their legally acceptable representatives.

ERB Ethics (or ethical) review board. An independent body constituted of medical, scientific.

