4.8.	Exploratory Estimand(s) and Analyses	16
4.9.	Supplementary Estimand(s) and Analyses	16
4.10.	Safety Analyses	17
4.10.1.	Extent of Exposure	17
4.10.2.	Adverse Events	17
4.10.3.	Clinical Laboratory Evaluations	20
4.10.4.	Vital Signs and Other Physical Findings	23
4.10.5.	Depression and Suicide	
4.11.	Other Analyses	25
4.11.1.	Concomitant Therapy	
4.11.2.	Treatment Compliance	
4.11.3.	Pharmacokinetics/Pharmacodynamics	
4.11.4.	Immunogenicity	
4.11.5.	Patient-Reported Outcomes	
4.11.6.	Subgroup analyses	
4.12.	CCI	
4.13.	Assessment Committee (AC) or Other Review Board	
4.14.	Changes to Protocol-Planned Analyses	
5.	References	29
Append	lix 1. Corticosteroid	30

Version History

This statistical analysis plan (SAP) for Study J1V-MC-IMMA is based on Protocol J1V-MC-IMMA, dated 22 Sept 2021.

SAP Version 2 was approved prior to the first unblinded interim analysis of the first Intervention Specific Appendix (ISA) (BT01). Changes in Version 2 are documented in the following table. Minor corrections and/or additions may not be included.

SAP Version History Summary

SAP Version	Approval Date	Change	Rationale
1		Not Applicable	Original version
2		Updated Section 1.2 Study Design Added detail to assignment to treatment, informed consent, and screening processes.	
		Updated Section 4 Statistical Analyses	
		Changes to layout	Ease of reading
		Additional detail included in 4.10.2.2, Serious Adverse Events.	
		Updated 4.10.3.1 Abnormal Hepatic Tests	

1. Introduction

This SAP is for Master Protocol Study J1V-MC-IMMA (IMMA). SAP IMMA has been developed after review of the J1V-MC-IMMA Clinical Study Protocol (final version dated 21 June 2021), and J1V-MC-IMMA Protocol Amendment (a) (final version dated 22 September 2021).

SAP IMMA describes the planned analysis of the efficacy and safety from this Master Protocol and its ISAs.

The intent of this document is to provide guidance for the statistical analyses of data. In general, the analyses are based on information from Protocol BT01 and there are no changes to the analyses described in the protocol. A limited amount of information concerning this study (for example, objectives, study design) is given to help the reader's interpretation.

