4.13. Assessment Committee (AC) or Other Review Board

Eligibility Review Committee

An eligibility review committee, also called adjudication panel, will review study entry data to ensure that prospective study participants meet the study entry criteria, particularly SLE disease activity criteria, prior to random assignment. In addition, the committee will help ensure that high quality data are entered into the EDC system for lupus assessments. The committee may include members of a third-party organization, members of the study team, and external SLE consultants as needed. Membership, responsibilities, operations, and measures to maintain confidentiality will be described in a committee charter.

Assessment Committee (AC)

In addition to safety reviews routinely performed by the sponsor as described in Master Protocol IMMA Section 8.2, the AC will review the safety data in an unblinded fashion periodically, or on an ad hoc basis during the study, and will determine whether any changes (for example, dose reductions or other protocol modifications) should be made. If an efficacy interim analysis is specified in an ISA, the AC will also be responsible for review of the available efficacy data. The AC reviewing the interim data will include, at a minimum, a Lilly medical physician, a statistician, and a representative from the Lilly Global Patient Safety Organization, and may include Lilly study team members. Details about the AC membership, purpose, responsibilities, and operation will be described in an AC charter, which will be approved prior to the first unblinding. Investigator sites will receive information about interim analysis results only if they need to know for the safety of their study participants.

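### SAP 4.13 lets Lilly study team members sit on the committee that sees unblinded data; protocol 10.1.5 forbids it, and the visible SAP text does not flag the change

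*SAP*

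**What the plan says.** The protocol addresses the committee in three places. Section 2.2.2 (Governance) creates it to assess safety data unblinded and states: "This internal committee will be independent of the Lilly study team". Section 8.2, under sponsor safety monitoring, gives its purpose: "The IAC is an advisory group for this study formed to protect the integrity of the study in unblinded safety data reviews". Section 10.1.5 lists the minimum members (a Lilly physician, a statistician and a patient safety representative) and adds "but will not include any Lilly study team members".

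SAP 4.13 gives the same list of minimum members and adds "and may include Lilly study team members".

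The SAP's version history ties it to the amended protocol that contains the exclusion: "This statistical analysis plan (SAP) for Study J1V-MC-IMMA is based on Protocol J1V-MC-IMMA, dated 22 Sept 2021". It also says that Version 2 was approved before the first unblinded interim analysis of BT01.

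**The concern.** In a double-blind trial, the list of people who may see results by arm is one of the main safeguards. The protocol uses an internal committee rather than an external one, so its protection rests on separating that committee from the people who run the study. The SAP sentence removes that separation.

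The committee's powers make this matter. Both documents let it decide whether the protocol should be modified, and both let it see efficacy data if an ISA specifies an efficacy interim. Study team members may also sit on the eligibility review committee ("The committee may include members of a third-party organization, members of the study team, and external SLE consultants as needed"), which confirms entry before randomization and helps ensure the quality of the lupus assessment data. Under the SAP, one person could hold both seats while enrollment continues.

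The reach may extend beyond BT01. Protocol 9.3.2.2 compares later interventions with all placebo data then available. Early knowledge of BT01 placebo results could therefore influence choices made for later ISAs, if the people making those choices had seen them.

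**Working it through.** No arithmetic applies. The check is a comparison of texts, followed by a search for any statement that reconciles them.

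**Step 1. Is it the same committee?** The name differs: Internal Assessment Committee in the protocol, Assessment Committee in the SAP. The content matches on every other element.

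| Element | Protocol 10.1.5 | SAP 4.13 |
|---|---|---|
| Safety review | Unblinded, periodic or ad hoc | Same |
| Authority | Decides whether protocol changes are needed | Same |
| Efficacy data | Reviewed if an ISA specifies an efficacy interim | Same |
| Minimum members | Physician, statistician, patient safety representative | Same |
| Charter | Approved before the first unblinding | Same |
| Information to sites | Only where participant safety requires it | Same |
| Study team members | "but will not include any Lilly study team members" | "and may include Lilly study team members" |

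That they are the same body is an inference from this parallel, but a strong one. Six elements agree and only the membership rule is reversed.

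**Step 2. Is the protocol's exclusion an isolated phrase?** No. Section 10.1.5 is the explicit membership ban. Section 2.2.2 reaches the same result by requiring independence from the study team. Section 8.2 gives the reason, which is to protect study integrity when data are reviewed unblinded.

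**Step 3. Does the SAP disclose the change?**
- The version history lists updates to Section 1.2, layout changes in Section 4, added detail in 4.10.2.2 and an update to 4.10.3.1. It does not mention committee membership. It warns that minor edits may be unlisted, but reversing a rule on access to unblinded data is not minor.
- SAP Section 1 and SAP 4.14 report no changes from the protocol. Both statements concern analyses, so neither is literally false about membership, but neither discloses the reversal.
- The content of SAP 4.12 and the protocol's interim analysis section (9.4 in its contents list) is withheld from the public versions. Non-disclosure is therefore established for the visible text only.

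**Step 4. When does the rule take effect?** SAP Version 2 was approved before the first unblinded BT01 interim, so the permissive wording was on file when that review fell due. The documents do not show who attended.

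**Step 5. Does it conflict with the protocol's definition of double-blind?** Protocol 10.10 says that those unaware of treatment are "neither the participant nor any of the investigator or sponsor staff who are involved in the treatment or clinical evaluation of the participants". The documents do not say which study team members fall in that group. One possible route is through the sponsor's medical monitors. Protocol 7.1 gives them a consulting role in whether a participant stays on study intervention, and protocol 9.3.1 counts permanent discontinuation as nonresponse. If those monitors are study team members, knowledge of results by arm could reach decisions that feed the endpoint. Whether they are is not stated.

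**The case against.** The strongest reply has four parts.

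1. A permission is not a requirement. A committee with no study team members would comply with both documents, the trial is to be run according to the protocol, and membership details are left to a charter approved before the first unblinding. On this view the conflict creates ambiguity, not access. It is true that no actual access has been shown. But the SAP still authorizes what the protocol prohibits, and an unseen charter cannot make both rules correct.

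2. Withheld sections may explain the difference. This stands as a limit on the claim of non-disclosure, which is confined here to the visible text. It does not affect the contradiction.

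3. The route to bias is not demonstrated. Assignment is computer-generated through the IWRS, the eligibility committee's entry review takes place before randomization, and sites receive interim information only when participant safety requires it. No passage says that study team members will plan later ISAs. These points stand, and the consequences above are stated conditionally for that reason.

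4. No estimand, endpoint, test or sample size changes. This is also true. It makes the problem a governance and blinding matter rather than an analysis error. It does not make it trivial, because confidence in any interim decision depends on knowing who was unblinded.

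**Conclusion.** The concern holds. SAP 4.13 permits study team members on the committee that reviews unblinded data. Protocol 10.1.5 bans them, protocol 2.2.2 requires the committee to be independent of them, and no visible text reconciles the positions. Measured against the protocol the SAP says it is based on, the SAP sentence is wrong as written.

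The problem has no numerical size. BT01's planned 90 or so participants, about 45 of them on placebo, give the scale of the data concerned but do not measure the effect of a membership rule. What is established is permitted exposure of results by arm to people the protocol keeps blinded, not bias that has occurred.

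The conclusion assumes that the two named committees are the same body, which the matching remit supports. It does not depend on the charter, the Unblinding Plan or the withheld sections. Those could add safeguards but could not remove the contradiction. Because the rule governs access to unblinded data and the correction is cheap, it should be treated as a required change.

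**What to change.** **Preferred.** Replace the permissive clause in SAP 4.13 with the protocol's exclusion, use one committee name in both documents, and confirm that the charter states the same rule. The cost is one SAP sentence, a naming correction and a charter check. The protocol needs no change to its rule.

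**If study team membership is intended.** Amend protocol 2.2.2 and 10.1.5, and record the change and its reason in the SAP. State which roles are unblinded, to what data and from when, and how those people are kept out of eligibility review, participant-level decisions and analysis choices for ongoing and later ISAs. The cost is an amendment to two protocol sections plus SAP and charter updates.

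**In either case.** If an unblinded review has already taken place under the current SAP wording, document which roles attended and what they saw, and report this in the BT01 clinical study report.

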Appendix 1. Corticosteroid

All corticosteroid doses need to be converted to prednisone equivalent doses (as detailed in Section 4.11.1). If additional conversion factors are required, these will be added to Table S1 in a SAP amendment prior to database lock. The following table should be used for converting nonprednisone medications to prednisone equivalent:

Multiply the dose of the corticosteroid taken by the patient (in milligrams) in Column 1 by the conversion factor in Column 2 to get the equivalent dose of prednisone (in milligrams).

Example: Patient is taking 16 mg of methylprednisolone po daily. To convert to prednisone: 16 mg methylprednisolone $\times 1.25 = 20 \text{ mg}$ prednisone. 16 mg of methylprednisolone per os daily is equivalent to 20 mg of prednisone po daily.

Table S1. Complete Conversion Factors for Calculating Prednisone (or Equivalent) Doses

Column 1	Column 2
Corticosteroid Preferred Term	Conversion factor for converting to an equivalent prednisone dose
Prednisone	1
Prednisone acetate	1
Prednisolone	1
Prednisolone acetate	1
Prednisolone sodium phosphate	1
Methylprednisolone	1.25
Methylprednisolone acetate	1.25
Methylprednisolone sodium succinate	1.25
Triamcinolone	1.25
Triamcinolone acetonide	1.25
Triamcinolone hexacetonide	1.25
Cortisone	0.2
Cortisone acetate	0.2
Hydrocortisone	0.25
Hydrocortisone acetate	0.25
Hydrocortisone sodium succinate	0.25
Betamethasone	6.25
Betamethasone acetate	6.25
Betamethasone dipropionate	6.25
Betamethasone sodium phosphate	6.25
Dexamethasone	6.25
Dexamethasone acetate	6.25

Column 1	Column 2
Corticosteroid Preferred Term	Conversion factor for converting to an equivalent prednisone dose
Dexamethasone phosphate	6.25
Dexamethasone sodium phosphate	6.25
Paramethasone	2.5
Deflazacort	0.83
Celestona bifas	6.25
Depo-medrol med lidokain	1.25
Diprospan	6.25
Fluocortolone	1
Meprednisone	1.25

Signature Page for VV-CLIN-117413 v1.0

Approval	PPD
	21-Aug-2023 11:51:56 GMT+0000

Signature Page for VV-CLIN-117413 v1.0
